Time to sustained recovery (improvement or resolution) of COVID-19 symptoms through Day 29: Defined as the time from the first dose date to the earliest date when sustained improvement or sustained resolution of COVID-19 symptoms is met (as detailed below) through Day 29. COVID-19 symptoms assessed include fever, chills, cough, sore throat, congestion, shortness of breath/difficulty breathing at rest, shortness of breath/difficulty breathing with exertion, muscle or body aches, fatigue, headache, nausea, vomiting, and diarrhea. Loss of taste/smell is excluded from this analysis.

Time to sustained improvement of COVID-19 symptoms through Day 29: Defined as the time from the first dose date to the first date when all of the above symptoms are scored as moderate or severe at baseline are scored as mild or absent, all of the above symptoms scored as mild or absent at baseline are scored as absent, and with no symptom worsening or new symptoms, except for cough, fatigue, and headache which may be mild or absent, through Day 29.

Time to sustained resolution of COVID-19 symptoms through Day 29: Defined as time from the first dose date to the first date when all of the above symptoms are scored as absent with no symptom recurrence or new symptoms, except cough, fatigue, and headache which may be mild or absent, through Day 29.

Censoring rules for time to COVID-19 symptoms through Day 29 analysis:

- Participants who are randomized but not treated are censored at Day 1.

- Participants who have any COVID-19-related hospitalization (≥ 24 hours) or all-cause death through Day 29 (as defined in the primary endpoint) will be censored at Day 30.
- Participants who have not been followed through Day 29 visit (discontinuation from study or incomplete follow-up at the time of analysis) will be censored at the last contact date.
- Participants who have completed the Day 29 visit and do not experience a defined event through Day 29 will be censored at Day 30.

[Table 2](#) provides further programming details.

Table 2: Criteria for Sustained Improvement and Sustained Resolution of COVID-19 Symptoms Through Day 29

COVID-19 Symptoms	Baseline Severity	Criteria for Sustained Improvement	Criteria for Sustained Resolution

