3.5.2. Virologic Endpoints

For all virologic assessments, the confirmatory retest (reflex) result should be used for analysis if present. If a participant has multiple assessments on the same date with different accession numbers, the accession number on the record with the highest viral load value should be used to select records for analysis. If viral load values are the same, the accession number on the record with the lowest value of MBSEQ will be used to select records for analysis.

Change from baseline in SARS-CoV-2 viral load (\log_{10} copies/mL) to Day 7 assessed by RT-qPCR from NP sample:

Change from baseline is defined as the viral load at the Day 7 assessment from NP sample minus the viral load at baseline from NP sample.

Viral load >5 (\log_{10} copies/mL) on Day 7 assessed by RT-qPCR from NP sample: A second cutoff of high viral load will also be examined: viral load >4 (\log_{10} copies/mL) on Day 7 assessed by RT-qPCR from NP sample.

Duration of SARS-CoV-2 viral shedding from Day 1 through Day 29 assessed by RT-qPCR from saliva samples: Duration of SARS-CoV-2 viral shedding will be analyzed based on the time to SARS-CoV-2 viral clearance, which is defined as time from the first dose date to the first date the viral load is not detected, ie, below the limit of detection (LOD), and sustained through Day 29. Participants who do not have the defined event or who discontinue study prior to Day 29 are censored at the earlier date of the last viral load assessment or Day 30. Deaths occurring prior to Day 29 will be censored at Day 30.

Change from baseline in SARS-CoV-2 viral load (\log_{10} copies/mL) to Days 3, 5, 7, 11, 14, 21, and 29 assessed by RT-qPCR from saliva samples: Change from baseline is defined as the viral load from saliva samples at the Day 3, 5, 7, 11, 14, 21, or 29 assessment minus the viral load from saliva sample at baseline.

Proportions of SARS-CoV-2 viral clearance (Days 3, 5, 7, 11, 14, 21, and 29) assessed by RT-qPCR from saliva samples: In the mFAS-S, the cumulative proportion of participants with viral clearance (viral load not detected and sustained through Day 29) at Days 3, 5, 7, 11, 14, 21, and 29 will be assessed by RT-qPCR from saliva samples. Participants who have died or discontinued study prior to Day 29 are assumed to have no viral clearance.

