
Time to sustained resolution in COVID-19 symptoms through Day 29 will be analyzed by KM methodology and stratified Cox Proportional Hazard model. Survival curves between ADG20 and placebo will be compared using a log-rank test stratified by age (categorical as 12-17, 18-65, and >65 years). A stratified Cox Proportional Hazard model will be used to estimate the hazard ratio where the model includes age (categorical as 12-17, 18-65, and >65 years) as stratification variable and sex (categorical), baseline serostatus (categorical), baseline BMI (continuous), and

baseline viral load (continuous as \log_{10} copies/mL) as covariates. Comparison of the survival distributions will use the score test for the hazard ratio from the Cox model.

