- c. If a participant discontinues from the study, is lost to follow up (LFU), or dies on or before Day 29, symptom ratings will not be imputed beyond the date of discontinuation/LFU/death.
- d. If diary data are missing when a participant is not COVID-related hospitalized and remains on study (through Day 29), data will be imputed as follows:
 - The Day 1 assessment is baseline and is performed on-site prior to study drug dosing, so the assessment is not likely to be missing. If data are present for Day 1 and is missing for a sequence of consecutive days from Day 1 but with at least one subsequent score, impute the missing values through to the first available score with the value of the first available score (provided by the participant or imputed due to hospitalization). This is a conservative assumption, so that symptom improvement or resolution is less likely to be indicated early.

- If only the Day 1 assessment is missing (for a given symptom), the value will be imputed as the Day 2 value.
- For intermittent missingness during follow-up, impute the missing values as the worse of the last available value (actually provided by the participant or imputed due to hospitalization) before the missing value and the first available value (actually provided by the participant or imputed due to hospitalization) after the missing value, irrespective of length of sequence of missing values. If the last prior and the first subsequent value are equal, then symptom improvement or resolution is based on the assumption that the situation remained stable during the missing duration. If the last prior value is worse than the first subsequent one, then symptom improvement/resolution is delayed over the missing duration until improvement/resolution is confirmed. If the last prior assessment is better than the first subsequent value, then symptom improvement/resolution is reversed earlier.

- e. If a participant has no period(s) of hospitalization and all post-Day 1 data are missing (for a given symptom) or all data, including Day1, are missing (for a given symptom), the symptom will not be imputed. If all data are missing for all symptoms, the participant will be excluded in the time-to-event analyses for improvement/resolution/sustained recovery.
- f. Missing data for the questions regarding sense of taste and smell, frequency of vomiting or diarrhea, will be imputed using the values mapped to none/mild/moderate/severe.

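### Participants who become symptom-free and then leave before Day 29 are censored at last contact, so key secondary 3 loses their events and counts their symptom-free days as unresolved time at risk; the bias depends on withdrawal by arm

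*SAP*

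**What the plan says.** The endpoint is time to sustained resolution of COVID-19 symptoms, third of the three key secondary endpoints in the hierarchy (SAP 4.4 and 5.5.3). SAP 3.5.1 dates the event to the "first date when all of the above symptoms are scored as absent with no symptom recurrence or new symptoms". Three symptoms (cough, fatigue and headache) are allowed to persist at a mild level, and the state must last until Day 29. The event date is therefore early, but the event can be confirmed only by follow-up to Day 29.

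The censoring rules in the same section treat two groups differently:

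- **Completers:** "Participants who have completed the Day 29 visit and do not experience a defined event through Day 29 will be censored at Day 30". This applies only if there was no event.
- **Early leavers** ("discontinuation from study or incomplete follow-up at the time of analysis) will be censored at the last contact date"). No such condition appears, and nothing is said about a participant who is already symptom-free.

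Appendix F, rule c, closes the other route to an event: after a participant leaves, "symptom ratings will not be imputed beyond the date of discontinuation/LFU/death".

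Under SAP 5.5.3 the hazard ratio comes from a Cox model stratified by age group, and the test is specified as follows: "Comparison of the survival distributions will use the score test for the hazard ratio from the Cox model".

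SAP 3.5.2 has a parallel rule for duration of viral shedding, where clearance must also be sustained through Day 29. Participants "who discontinue study prior to Day 29 are censored at the earlier date of the last viral load assessment or Day 30".

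**The concern.** Censoring at time t tells the model that the event had not happened by t. Take a participant whose diary is clear from Day 6 and who withdraws on Day 20. The resolution time is Day 6 if nothing recurred, and unknown otherwise. The rule nevertheless keeps this participant in the risk set as unresolved for 20 − 6 = 14 days, against the diary. If the last contact is later than the last diary entry, the false at-risk time is longer still.

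Two things go wrong: an event is discarded, and the risk set is inflated with people who have already resolved. The faster-recovering arm has more such people, so even random withdrawal at the same rate in both arms does not cancel out of the hazard ratio. If withdrawal differs between arms, the arm with more withdrawal looks slower to recover whether or not the drug works.

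No planned analysis tests the rule. The multiple imputation in SAP 5.5.3.1 covers only the two binary key secondaries. The per-protocol repeat can drop early leavers, because SAP 4.5.5 requires a known primary endpoint. Appendices H and I define no estimand for this endpoint.

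**Working it through.** **Inputs.** From the documents: about 320 participants in the primary efficacy population, allocation 1:1 (SAP 4.2), two-sided 0.05, Cox score test. The plan gives no hazard ratio, median, power or withdrawal rate for this endpoint, so there is no stated figure to reproduce. Assumed: exponential resolution times with medians of 10 days (ADG20) and 14 days (placebo), true HR 14/10 = 1.40; withdrawal uniform over Days 2 to 29 and unrelated to outcome; no relapse. An HR above 1 favours ADG20.

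**Why the bias arises.** In one arm let λ be the resolution hazard, S(t) the proportion unresolved, W(t) the proportion not yet withdrawn and G the proportion who stay to Day 29.

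- Only stayers can have an event, so events occur at rate λ·S·G.
- Under the SAP rule the risk set is S·W (unresolved) plus (1 − S)(W − G) (resolved, will withdraw later), which simplifies to W − G + G·S.
- Apparent hazard, SAP rule: λ·G·S / (W − G + G·S). The multiplier depends on S, so it differs between arms even when withdrawal is equal.
- Apparent hazard when censoring at the last symptomatic day: λ·G/W. The multiplier cancels between arms if withdrawal is equal. It is still below 1, so the medians stay too long.

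**Numbers at Day 10, 10% withdrawal in both arms.** W = 1 − 0.10 × 8/27 = 0.970, G = 0.90, W − G = 0.070. ADG20: S = 0.500, multiplier 0.450/0.520 = 0.865. Placebo: S = 2^(−10/14) = 0.610, multiplier 0.549/0.619 = 0.886. Apparent HR = 1.40 × 0.865/0.886 = 1.37.

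**Numbers at Day 10, true HR 1.0 (both medians 14), 5% ADG20 / 10% placebo.** ADG20: W = 0.985, G = 0.95, multiplier 0.579/0.614 = 0.943. Apparent HR = 0.943/0.886 = 1.06. With last-symptomatic-day censoring it is (0.95/0.985)/(0.90/0.970) = 1.04, so that rule corrects only part of the error.

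**Large-sample simulation over the whole period, equal withdrawal, true HR about 1.40:**

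| Withdrawal | Handling | HR | z at N = 320 | Medians (days) |
|---|---|---|---|---|
| 0% | any | 1.40 | 2.67 | 10 / 14 |
| 5% | SAP rule | 1.38 | 2.53 | – |
| 10% | SAP rule | 1.37 | 2.40 | about 11.5 / 15.7 |
| 10% | censor at last symptomatic day | 1.40 | 2.54 | about 11.0 / 15.2 |
| 10% | event at first symptom-free day | 1.40 | 2.63 | 10.1 / 14.1 |
| 15% | SAP rule | 1.35 | 2.22 | – |

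Approximate power is Φ(z − 1.96): Φ(0.71) = 76% with no withdrawal, Φ(0.57) = 72% at 5% and Φ(0.44) = 67% at 10% under the SAP rule. About 56% of withdrawals had already resolved, so at 5% the number affected per arm is 160 × 0.05 × 0.56, or 4 to 5 people.

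**Unequal withdrawal:**

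| True HR | ADG20 / placebo | SAP rule | Last symptomatic day |
|---|---|---|---|
| 1.40 | 5% / 10% | 1.46 | 1.45 |
| 1.40 | 5% / 15% | 1.55 | 1.51 |
| 1.0 | 5% / 10% | about 1.05 | about 1.03 |
| 1.0 | 5% / 15% | about 1.11 | about 1.07 |
| 1.0 | 10% / 5% | 0.95 | 0.97 |

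For the null rows at 5%/10% and 5%/15%, two-sided rejection at 320 participants is about 7% and 13% under the SAP rule, and about 6% and 8% with last-symptomatic-day censoring. Counting the event at the first symptom-free day recovers the true HR throughout, but only because the model has no relapse after withdrawal. With equal withdrawal and no effect, the HR stays at 1.00 under every rule.

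Hospitalization, death, relapse and diary rounding were not modelled. Simulation error on the HR is about 0.005 to 0.01.

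**The case against.** **Not crediting an unconfirmed resolution is a defensible conservative choice.** The endpoint requires absence of symptoms to Day 29, and for a leaver that is unobserved. This stands as far as withholding the event goes, and under equal withdrawal there is no false-positive risk. It does not justify adding observed symptom-free days to the risk set as unresolved.

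**Few people are affected.** Protocol 4.2.2 asks sites to seek Day 29 assessments from those who withdraw and delays the lost-to-follow-up label, and SAP 3.2 holds the soft lock until Day 29 visits are complete. This stands: at 5% equal withdrawal the HR moves by about 1%.

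**Censoring at the last symptomatic day is not a cure.** It is informative censoring too, removes only part of the error in the medians, and corrects the HR fully only when withdrawal is equal. When placebo withdrawal is only slightly higher, the two errors in the SAP rule happen to offset and the replacement can be marginally further from the truth: for true HR 1.50 with 5% ADG20 / 7% placebo, 1.52 against 1.51. This stands, and is why the sensitivity analysis is needed alongside it.

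**A reader might infer that the hazard ratio is necessarily biased toward 1, or conversely that type I error is inflated.** The documents support neither. The first needs a true effect and similar withdrawal, the second needs unequal withdrawal, and no rate is given overall or by arm.

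**Conclusion.** The defect is in the text: for early leavers, the SAP discards resolutions seen in the diary and analyses the following symptom-free days as unresolved. The direction and size of the resulting bias are conditional. With a real effect and similar withdrawal, the HR is attenuated by roughly 1% at 5% withdrawal and 2% at 10%, approximate power falls by about 4 and 9 percentage points, and both medians lengthen (by about 1.5 days at 10%). With unequal withdrawal the HR can move either way, including away from 1 when there is no effect, which matters more for an alpha-controlled endpoint. All sizes rest on the assumed medians, uniform non-informative withdrawal and no relapse. If few participants withdraw, the effect is small.

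The same logic applies to viral shedding, but that is a non-key endpoint with nominal p-values only (SAP 4.4 and 5.5.4), and its size was not computed. It should not be read as a threat to the testing hierarchy.

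**What to change.** Before unblinding:

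1. In SAP 3.5.1, for participants not followed through Day 29, replace the last contact date with the last diary day on which the criterion was not met. State that this preserves the HR only under equal withdrawal.
2. In SAP 5.5.3.1, add a sensitivity analysis for key secondary 3 that counts the event at the first qualifying day if the criterion then held to the last diary entry. State that it assumes no relapse after withdrawal.
3. Report, by arm, the number of early leavers and how many were already symptom-free when they left. This shows whether the bias is material and in which direction.
4. In SAP 3.5.2, for participants who discontinue before Day 29, censor viral shedding at the last sample with detected virus.

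The cost is SAP wording, minor programming and one extra analysis, with no new data. A few participants will have earlier censoring dates.

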3.5.2. Virologic Endpoints

For all virologic assessments, the confirmatory retest (reflex) result should be used for analysis if present. If a participant has multiple assessments on the same date with different accession numbers, the accession number on the record with the highest viral load value should be used to select records for analysis. If viral load values are the same, the accession number on the record with the lowest value of MBSEQ will be used to select records for analysis.

Change from baseline in SARS-CoV-2 viral load (\log_{10} copies/mL) to Day 7 assessed by RT-qPCR from NP sample:

Change from baseline is defined as the viral load at the Day 7 assessment from NP sample minus the viral load at baseline from NP sample.

Viral load >5 (\log_{10} copies/mL) on Day 7 assessed by RT-qPCR from NP sample: A second cutoff of high viral load will also be examined: viral load >4 (\log_{10} copies/mL) on Day 7 assessed by RT-qPCR from NP sample.

Duration of SARS-CoV-2 viral shedding from Day 1 through Day 29 assessed by RT-qPCR from saliva samples: Duration of SARS-CoV-2 viral shedding will be analyzed based on the time to SARS-CoV-2 viral clearance, which is defined as time from the first dose date to the first date the viral load is not detected, ie, below the limit of detection (LOD), and sustained through Day 29. Participants who do not have the defined event or who discontinue study prior to Day 29 are censored at the earlier date of the last viral load assessment or Day 30. Deaths occurring prior to Day 29 will be censored at Day 30.

Change from baseline in SARS-CoV-2 viral load (\log_{10} copies/mL) to Days 3, 5, 7, 11, 14, 21, and 29 assessed by RT-qPCR from saliva samples: Change from baseline is defined as the viral load from saliva samples at the Day 3, 5, 7, 11, 14, 21, or 29 assessment minus the viral load from saliva sample at baseline.

Proportions of SARS-CoV-2 viral clearance (Days 3, 5, 7, 11, 14, 21, and 29) assessed by RT-qPCR from saliva samples: In the mFAS-S, the cumulative proportion of participants with viral clearance (viral load not detected and sustained through Day 29) at Days 3, 5, 7, 11, 14, 21, and 29 will be assessed by RT-qPCR from saliva samples. Participants who have died or discontinued study prior to Day 29 are assumed to have no viral clearance.

Proportion of SARS-CoV-2 viral load BLQ/not detected or not detected at Day 7 assessed by RT-qPCR from NP samples: In the mFAS-NP, the proportion of participants with viral load BLQ/not detected or not detected at Day 7 assessed by RT-qPCR from NP samples.

SARS-CoV-2 viral load AUC assessed by RT-qPCR from saliva samples through Day 29: Defined as AUC of SARS-CoV-2 viral load from baseline through Day 29 from saliva samples at Days 3, 5, 7, 11, 14, 21, and 29. AUC is calculated using the trapezoidal method.

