Viral load >5 (\log_{10} copies/mL) on Day 7 (± 1) based on NP samples	Same as primary efficacy analysis (see Section 7.6). Analysis will be performed in mFAS-non-Omicron-NP with available data at Day 7. Analysis will be repeated using a second definition of high viral load (viral load $>4 \log_{10}$ copies/mL).

Endpoint	Statistical Analysis Methods
Duration of SARS-CoV-2 viral shedding from Day 1 through Day 29 assessed by RT-qPCR from saliva samples	KM methodology will be used to analyze duration of viral shedding from Day 1 through Day 29 by SARS-CoV-2 RNA defined as time from the first dose date to the first date the viral load is not detected, ie, below the limit of detection (LOD), and sustained through Day 29. KM curves will be compared between ADG20 and Placebo using a log-rank test stratified by age (categorical). A stratified Cox Proportional Hazard model will be used to estimate the hazard ratio where the model includes age (categorical as 12-17 years, 18-65 years and >65 years) as stratification variable and sex (categorical), baseline serostatus (categorical as positive; negative), baseline BMI (continuous) and baseline viral load (continuous as \log_{10} copies/mL) as covariates. Comparison of the survival distributions will use the score test for the hazard ratio from this Cox model. Analyses will be performed on the mFAS-non-Omicron-S. Deaths occurring prior to achieving cessation of viral shedding will be censored at Day 30.
Change from baseline in SARS-CoV-2 viral load (\log_{10} copies/mL) to Days 3, 5, 7, 11, 14, 21, and 29 assessed by RT-qPCR from saliva samples	Observed saliva baseline and post-baseline values are used to calculate change from baseline. Mixed model for repeated measures with treatment group and the prognostic factors (with observed saliva baseline) in the primary efficacy endpoint analysis as covariates will be performed. The LS mean for the point estimate in each group and 95% CIs will be presented. The difference in LS means between the ADG20 group and the placebo group and the 95% CIs for the differences will be determined. A plot of the LS means with 95% CIs by day assess by treatment group will be presented. The analysis will be performed on the mFAS-non-Omicron-S with available data at each timepoint. In addition, a two-sample t-test will be used to compare change from baseline viral load between treatment at each time point without covariate adjustment (unadjusted mean difference).

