4. GENERAL STATISTICAL CONSIDERATIONS

4.1. General Rules and Considerations

Continuous variables will be summarized using the following descriptive summary statistics: the number of participants (n), mean, SD, median, first and third quartiles, minimum (min), and maximum (max).

Categorical variables will be summarized using frequency counts and percentages.

Baseline value, unless specified otherwise, is defined as the last non-missing measurement (scheduled or unscheduled) collected on or before the dose of study drug. If the date of dosing is missing, the date of randomization will be used instead.

Unless otherwise specified, the display precision for the summary statistics of all numerical variables will follow programming standards. Please see [Appendix A](#) for variable display standards.

When count data are presented, the percentage will be suppressed when the count is zero in order to draw attention to the non-zero counts. A row denoted “Missing” will be included in count tabulations as needed to account for dropouts and missing values. The denominator for all percentages will be the number of participants in the treatment group within the analysis set of interest, unless otherwise specified.

Change from baseline is defined as the value at the post-baseline visit minus the value at the baseline visit.

Study Day 1 is the calendar day that study drug is administered. Subsequent study days are calculated as the date of assessment/event – date of injection + 1. If a participant is not dosed, the date of randomization is used to define Study Day rather than the date of injection.

Time-to-event variables are defined from the date of dosing. If a participant is not dosed, the date of randomization is used.

All summaries involving diary data will be based on distinct diary date entries.

Unscheduled visits: Unscheduled visit measurements will be included in the analysis as follows:

- In scheduled visit windows per specified visit windowing rules.
- In the derivation of baseline measurements.
- In the derivation of maximum/minimum change from baseline values and worst post-baseline values for safety analyses.
- In individual participant data listings as appropriate.

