Change from baseline in SARS-CoV-2 viral load (\log_{10} copies/mL) to Day 7 (± 1) assessed by RT-qPCR from NP samples	
Observed NP baseline and post-baseline values are used to calculate change from baseline. ANCOVA with treatment group and the prognostic factors (with observed NP baseline) as in the primary efficacy endpoint analysis as covariates. The LS mean for the point estimate in each group and 95% CIs will be presented. The difference in LS means between the ADG20 group and the placebo group and 95% CIs for the differences will be determined. The analysis will be performed on the mFAS-non-Omicron-NP with available data at Day 7. In addition, two-sample t-test will be used to compare change from baseline viral load between treatment without covariate adjustment (unadjusted mean difference).
 
If Day 7 value is missing, the earliest measurement closest to the Day 7 visit within 1 day (including scheduled and unscheduled visit) will be used.

Viral load >5 (\log_{10} copies/mL) on Day 7 (± 1) based on NP samples	The methods for the primary efficacy endpoint will be used. Analysis will be performed on the mFAS-non-Omicron-NP with available data at Day 7. Analysis will be repeated using a second definition of high viral load (viral load $>4 \log_{10}$ copies/mL).
Duration of SARS-CoV-2 viral shedding from Day 1 through Day 29 assessed by RT-qPCR from saliva samples	KM methodology will be used to analyze duration of viral shedding from Day 1 through Day 29 of SARS-CoV-2 RNA. KM curves, the number and percentage of censored observations and the median, 25 th and 75 th percentiles will be provided. Survival distributions will be compared between ADG20 and placebo using a log rank test stratified by age (categorical) and baseline serostatus. A stratified Cox Proportional Hazard model will be used to estimate the hazard ratio where the model includes age (categorical as 12-17 years, 18-65 years and >65 years) as a stratification variable and sex (categorical), baseline serostatus (categorical as positive; negative), baseline BMI (continuous) and baseline viral load (continuous as \log_{10} copies/mL) as covariates. Comparison of the survival distributions will use the score test for the hazard ratio from this Cox model. Analyses will be performed on the mFAS-non-Omicron-S.

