APPENDIX B. ANALYSIS VISIT WINDOWS

Assessments collected at scheduled or unscheduled visits will be mapped using the analysis visit windows listed in [Table 10](#). All diary data will be analyzed using the actual day. Refer also to Section [4.1](#).

Table 10: Analysis Windows

AVISIT	AVISITN	Range of Trial Day	Target Day	If more than one value, which value is used for analyses
Screening	1	Day -2 to 1		Last value prior to administration of study drug
Day 1	2	Day 1	Day 1	Day 1
Day 3	4	Day 2 to Day 4	Day 3	Nominal visit. If none exist, then closest to target day.
Day 5	6	Day 4 to Day 6	Day 5	Nominal visit. If none exist, then closest to target day.
Day 7	8	Day 6 to Day 8	Day 7	Nominal visit. If none exist, then closest to target day.
Day 11	12	Day 9 to Day 13	Day 11	Nominal visit. If none exist, then closest to target day.
Day 14	15	Day 12 to Day 16	Day 14	Nominal visit. If none exist, then closest to target day.
Day 21	22	Day 18 to Day 23	Day 21	Nominal visit. If none exist, then closest to target day.
Day 29	30	Day 24 to Day 34	Day 29	Nominal visit. If none exist, then closest to target day.
Day 60	31	Day 53 to Day 67	Day 60	Nominal visit. If none exist, then closest to target day.
Day 90	32	Day 76 to Day 104	Day 90	Nominal visit. If none exist, then closest to target day.
Month 6	33	Day 150 to Day 210	Day 180	Nominal visit. If none exist, then closest to target day.
Month 11	34	Day 300 to Day 360	Day 330	Nominal visit. If none exist, then closest to target day.
Month 14	35	Day 360 to Day 480	Day 420	Nominal visit. If none exist, then closest to target day.

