ⁱ Participants will complete the daily COVID-19 Symptom Diary (includes global impression questions) Day 1 through Day 29. The Injection Site Reaction Diary will be completed Day 1 through Day 4. Site will provide a ruler along with instructions regarding completion of the Injection Site Reaction Diary (protocol Appendix 12.3). Instruct participants to record any local ISRs daily through Day 4.

^j Perform vital signs before, during, and after study drug administration per protocol Section 6.4.1. Protocol Section 6.4.1 outlines required vital signs on Day 1, duration of monitoring post-dose, and ISR monitoring and management.

^k Record information regarding participant survival and participant medically attended visits (telemedicine, physician office, urgent care center, emergency room, hospitalization) and relationship of medically attended visits to COVID-19. During telemedicine visits, the participant will also be reminded to complete daily COVID-19 Symptom Diary, daily temperature, blood oxygen saturation and heart rate, and saliva sample collection on the appropriate days.

^l Participants will collect their own saliva sample using the collection materials provided on Days 3, 5, 11, 14, and 21 and return them to the study site according to provided instructions. Note: Day 7 and Day 29 are in-clinic or home health visits and the saliva sample will be collected and transported by site staff or delegate. Participants should NOT eat, drink, smoke, or chew gum for 30 minutes before sample collection. The sample will be used for SARS-CoV-2 RT-qPCR and may be used for viral sequencing. In the event of worsening COVID-19 or potential relapse or re-infection, a saliva sample for SARS-CoV-2 RT-qPCR and sequencing should be collected as described in protocol Section 6.8.1.

^m Participants will be asked to monitor temperature, blood oxygen saturation, and heart rate at approximately the same time each day. Additional measurements may be taken at other times during the day if the participant feels feverish or short of breath at rest.

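### Viral shedding: clearance can be dated up to Day 34 but non-clearance is censored by Day 30, so the Kaplan-Meier tail can be forced to full clearance and a true hazard ratio diluted

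*SAP*

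**What the plan says.** SAP 3.5.2 (Virologic Endpoints) analyses shedding as time to clearance, where the event is the "first date the viral load is not detected, ie, below the limit of detection (LOD), and sustained through Day 29". SAP 4.1 adds that "Time-to-event variables are defined from the date of dosing". No upper limit is placed on the event date.

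Censoring does have a limit. Participants without clearance, or who leave before Day 29, "are censored at the earlier date of the last viral load assessment or Day 30". For deaths the SAP states: "Deaths occurring prior to Day 29 will be censored at Day 30". Protocol 7.8 has a similar rule: "Deaths occurring prior to achieving cessation of viral shedding will be censored at Day 30".

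The last saliva sample is tied to a visit. According to SAP Appendix M, "Day 7 and Day 29 are in-clinic or home health visits and the saliva sample will be collected and transported by site staff or delegate". The visit window in that appendix and in Protocol Table 12-1 is +5 days, so the sample date is Day 29 to Day 34. SAP Appendix B maps "Day 24 to Day 34" to the Day 29 visit.

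SAP 5.5.4, Table 4, plans Kaplan-Meier curves with median and quartiles, a log-rank test and a stratified Cox model: "Comparison of the survival distributions will use the score test for the hazard ratio from this Cox model".

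**The concern.** Follow-up time at the last visit depends on the result. Two participants sampled on Day 33 get different times: 33 if the sample is negative, 30 if it is positive. From Day 31 the risk set contains only people who are going to clear, because every persistent shedder and every death has already left it.

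The curve and its upper percentiles would then describe visit scheduling rather than virus. The clearances dated late would add almost nothing to the comparison between arms. The plan could also report, for example, about 70% cleared by visit in its companion clearance endpoint beside a shedding curve that ends at 100% cleared.

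**Working it through.** The documents give no hazard ratio, event count or power for this endpoint, so there is no stated figure to reproduce. The check has two parts.

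**1. Logic.** Kaplan-Meier multiplies the factors (1 − events / number at risk). Suppose 10 participants in an arm remain uncleared before the last visit; 6 never clear and are censored by Day 30, and 4 clear on Days 31, 32, 33 and 34. The factors are 3/4, 2/3, 1/2 and 0, so the curve reaches 0% still shedding although 6 of the 10 never cleared. Dating all 10 at one end point gives 1 − 4/10 = 60% of them still shedding. The forced zero needs only one event dated Days 31-34 in the arm.

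**2. Simulation.** From the documents: visits on Days 3, 5, 7, 11, 14, 21 and 29 within their windows, with the last on Days 29-34, and the event and censoring rules above. Assumed: Weibull clearance (shape 1.5); placebo clearance by Day 29 of 50%, 70% or 90%; 67%, 30% or 10% of Day 29 visits on Days 31-34; 150 per arm. The size of the saliva analysis set is not given; SAP 4.2 puts the whole primary efficacy population at about 320, or 160 per arm. The comparison rule gives events and censoring a common cap at Day 30. Each cell has 400 replicates, so power near 80% has a Monte Carlo standard error of √(0.8 × 0.2 / 400) = 2 points.

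True hazard ratio 1.5; loss = 1 − (HR as written / HR common end point):

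| Placebo cleared by Day 29 | Visits after Day 30 | HR as written | HR common end point | Loss | Log-rank power, written vs common |
|---|---|---|---|---|---|
| 50% | 67% | 1.366 | 1.507 | 9.4% | 62% vs 81% |
| 50% | 30% | 1.442 | 1.506 | 4.2% | 71% vs 79% |
| 50% | 10% | 1.477 | 1.501 | 1.6% | 72% vs 75% |
| 70% | 67% | 1.377 | 1.491 | 7.6% | 75% vs 87% |
| 70% | 30% | 1.424 | 1.479 | 3.7% | 78% vs 86% |
| 70% | 10% | 1.483 | 1.508 | 1.7% | 86% vs 87% |
| 90% | 67% | 1.427 | 1.473 | 3.1% | 85% vs 91% |
| 90% | 30% | 1.444 | 1.469 | 1.7% | 87% vs 90% |
| 90% | 10% | 1.473 | 1.490 | 1.1% | 88% vs 90% |

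- **True hazard ratio 2.0** (150,000 per arm): 1.70 to 1.94 as written, against 1.95 to 2.01. The largest loss is 1 − 1.696/1.981 = 14%; with 10% late visits it is about 2-3%.
- **True hazard ratio 1.0:** no bias, and rejection as written is 3.5-6.0%.
- **Curve:** it reached 100% clearance in 99-100% of simulated arms when 30% or 67% of visits were late, and in 90-98% when 10% were. With the common end point it ended at about 51-54%, 71-74% and 90-92% for the three clearance rates.
- **Percentiles:** the 75th percentile and the tail are exposed. The median is affected only if fewer than half have cleared by Day 30.

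**The strict reading.** If events dated after Day 29 are not counted, the hazard ratio is 1.47-1.51 for a true 1.5 and the curve is not forced to zero. However, the final cleared share is understated. With 70% placebo clearance and a true hazard ratio of 1.5, it ends at 55% against 74% under the common end point (67% late visits), or 65% against 71% (10% late).

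**The case against.** The best defence is that the endpoint is named for the period through Day 29. SAP 3.5.1 defines that phrase, for the primary endpoint, as running up to and including Day 29. With that limit on events, censoring at Day 30 is coherent and neither effect arises. This stands as a possible reading, so the forced curve and the dilution cannot be called certain. But the definition is given only for the primary endpoint. Carried over here, it would treat anyone who first clears at a Day 30-34 visit as still shedding, although Appendix B accepts that visit as the Day 29 assessment. The Appendix B mapping does not settle the matter either: it assigns visit labels, while event times run on actual dates.

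The effect may also be small. Clinics may hold most Day 29 visits on time, and then the hazard ratio loses only 1-3%. That stands for the hazard ratio. It helps the curve much less, because a single late event in an arm is enough.

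Finally, the endpoint is descriptive, and the plan also reports the number censored and the cumulative clearance by visit, with deaths and dropouts counted as not cleared. A careful reader could spot the mismatch. That limits the harm but does not make the curve right.

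A reader might infer that the treatment comparison is invalid or biased toward a false positive. The documents do not support that: both arms follow the same rule, the simulated null rate is unaffected, and any distortion of the hazard ratio is toward no effect.

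**Conclusion.** The concern holds in this form: the written rule lets clearance be dated later than non-clearance at the same visit. In any arm with a first clearance dated Days 31-34, the Kaplan-Meier curve then ends at 0% still shedding regardless of the true share. If there is a treatment effect, the hazard ratio shrinks by about 1-3% when 10% of Day 29 visits are late, and by up to about 9% (true hazard ratio 1.5) when two thirds are. Those sizes rest on assumed clearance rates, effect sizes and visit timing, none of which the documents give; the fall of the curve follows from the rule alone.

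A reader might extend this to the trial's main result. That is not supported: this is a non-key secondary endpoint with nominal p-values, and neither the primary analysis nor the hierarchical tests use this rule. It should be corrected, but it does not threaten the primary conclusion.

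**What to change.** In SAP 3.5.2, and by the same words in Table 4, state one end point:

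- Clearance first seen at the Day 29 visit (through Day 34) is dated Day 29.
- Participants who complete that visit without clearance, and all deaths before clearance, are censored at Day 30.
- Other discontinuations are censored at their last viral load date.

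Using actual last sample dates for non-clearers, with deaths at Day 35, is not an adequate substitute. Non-clearers seen early still leave the risk set before later clearers, so clearance stays overstated. In one simulated setting (50% placebo clearance, 67% late visits), actual last sample dates showed 74% cleared at Day 34 against 54% under the common end point.

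The cost is a short addition to the SAP text and one derivation change. It needs no new data and can be made blind before the SAP is signed.
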